#### **12.1.4 Evaluation of Possible Presence of NSCs and/or hCE1m6 in the Systemic Circulation Using QPCR**

An evaluation of possible presence of NSCs and/or hCE1m6 in the systemic circulation will be performed in the CICSL by quantitative PCR using established laboratory SOP and primer pairs specific for the *vMyc* gene and CD. For example, a standard curve will be generated using DNA isolated from the administered NSCs titrated into DNA from PBMCs (negative for *vMyc*); in parallel reactions, DNA isolated from patient samples will be subjected to amplification. The % NSC DNA (i.e. the % of total nucleated cells in samples that contain *vMyc* DNA) in patient PBMC samples will be determined from the standard curve. A parallel set of amplification reactions using genomic p21 primers (amplifying equivalently from all samples) will be used to normalize across samples.

#### **12.1.5 Assessment of Serum Cytokine Levels in the Event that a Patient Develops a Suspected Immune Response to the NSCs**

The Human Cytokine Thirty-Plex Antibody Bead Kit (Invitrogen, Camarillo, CA) will be used to analyze serum samples for 30 cytokines: epidermal growth factor (EGF); eotaxin; basic fibroblast growth factor (FGF-basic); granulocyte colony-stimulating factor (G-CSF); granulocyte macrophage colony-stimulating factor (GM-CSF); hepatocyte growth factor (HGF); interferon alpha (IFN- $\alpha$ ); IFN-gamma ( $\gamma$ ); interleukin-1 beta (IL-1 $\beta$ ); interleukin-1 receptor antagonist (IL-1RA); IL-2; interleukin-2 receptor (IL-2R); IL-4; IL-5; IL-6; IL-7; IL-8; IL-10; IL-12p40/p70; IL-13; IL-15; IL-17; IFN-  $\gamma$ -inducible protein 10 (IP-10); monocyte chemoattractant protein-1 (MCP-1); monokine induced by IFN-  $\gamma$  (MIG); monocyte inflammatory protein-1 alpha (MIP-1 $\alpha$ ); monocyte inflammatory protein-1 beta (MIP-1 $\beta$ ); regulated upon activation, normal T-cell expressed and secreted cytokine (RANTES); tumor necrosis factor (TNF)- $\alpha$ ; and vascular endothelial growth factor (VEGF). The assay plate will then be transferred to the Bio-plex HTF Luminex System (Bio Rad Laboratories, Inc., Hercules, CA) instrument for analysis. Cytokine concentrations will be calculated using Bio-plex Manager 3.0 Software with a 5 parameter curve-fitting algorithm applied for standard curve calculations for duplicate samples.

#### **12.1.6 Replication Competent Retrovirus (RCR) Testing**

The City of Hope CICSL will process samples, with DNA being isolated and stored, according to established laboratory SOP, until RCR testing is performed by PCR. Samples will be taken at 3 months, 6 months, and annually thereafter until their passing or withdrawal from follow-up.

## Brain Tissue Correlates

---

### 12.1.7 Determining the Fate of the NSCs at the time of Autopsy

---

As part of the consenting process, study patients will be asked to give permission for a brain autopsy. The brain autopsy will focus on detecting the presence or absence of NSCs, their location, and tumor pathology. Specifically, brain tissue samples will be collected from the center and periphery of the tumor, as well as grossly affected and unaffected areas from distant and contralateral sites. Tissue samples will be formalin fixed and paraffin embedded for sectioning and analysis. When possible, fresh frozen tissue samples will be taken. NSCs will be detected by PCR methods using specific primers for *v-myc* (only present in the transplanted NSCs). Fluorescence *in situ* hybridization and immunocytochemistry techniques will be used for the detection and further characterization of the NSCs (including proliferation and differentiation markers). We will also look for the presence of hCE1m6 in brain tissue samples.

### 12.1.8 Collecting Tumor Tissue for Future Research

---

If there is resection material available in excess of that needed for standard pathologic studies, this excess material will be used for research purposes.

Excess surgical material will be grown as a dissociated primary cell culture in the [name] laboratory for NSC migration and toxicity assays under City of Hope IRB#07047. Additional material will be banked (fixed and frozen) for potential future research under IRB #07047. Such research may include: 1) comparison of gene expression profiles in the tumor and adjacent tissue (if available) prior and after treatment with HB1.F3.CD.CE/irinotecan; 2) presence of immune cells (B-cells, T-cells, macrophages, microglia, dendritic cells); 3) determination of mitotic index in the tumor by Ki67 immunohistochemistry.

## 13 ENDPOINT EVALUATION CRITERIA/MEASUREMENT OF EFFECT

---

### Response Criteria

---

The Response Assessment in Neuro-Oncology (RANO) criteria (Wen et al., 2010) will be used to assess response:

**Complete Response (CR)** Complete disappearance of all enhancing disease (measurable and non-measurable) that is sustained for at least 4 weeks, stable or improved non-enhancing FLAIR/T2 lesions, no new lesions, off corticosteroids (physiologic replacement doses allowed), and neurologically stable or improved.

**Partial Response (PR)**  $\geq 50\%$  decrease of all measurable enhancing lesions, sustained for at least 4 weeks, no progression of non-measurable disease, stable or improved non-enhancing FLAIR/T2 lesions, no new lesions, corticosteroid dose stable or reduced (compared to baseline), and neurologically stable or improved.

**Stable Disease (SD)** Does not qualify for CR, PR, or PD, stable non-enhancing FLAIR/T2 lesions, stable or reduced corticosteroids (compared to baseline), clinically stable.

**Progressive Disease (PD)**  $\geq 25\%$  increase in enhancing lesions despite stable or increasing steroid dose, increase (significant) in non-enhancing T2/FLAIR lesions that is not attributable to other non-tumor causes, any new lesions, clinical deterioration (not attributable to other non-tumor causes and not due to steroid decrease).

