### **Secondary Objectives**

- To describe the relationship between hCE1m6-NSC dose and SN-38 concentrations in brain interstitium.
- To characterize the relationship between intracerebral and systemic concentrations of irinotecan and SN-38.
- To investigate the biologic activity of hCE1m6 NSCs by comparing SN-38 concentrations in the brain after treatment with hCE1m6-NSCs and irinotecan versus irinotecan alone.
- To assess for possible development of adenovirally transduced NSC immunogenicity after first exposure and with repeat doses of NSCs.
- To describe the clinical benefit (defined as stable disease, partial response, or complete response) in patients who receive treatment with repeat cycles of NSCs and irinotecan.
- To determine, at time of autopsy, the fate of the NSCs.

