- b. To be performed within 14 days from planned date of surgery, except for MRI (footnote ee) to be performed within 28 days of registration.
- c. Laboratory evaluations to be performed and results reviewed within 2 days prior to agent administration. Laboratory evaluations may be performed at a clinic local to the participant.
- d. 'Start of Cycle' criteria are found in Section 7.2.2. All assessments to occur prior to administration of NSCs (or irinotecan for dose levels 1/-1).
- e. All assessments to occur prior to administration of NSCs (or irinotecan for dose levels 1/-1).
- f. Imaging (brain MRI and PET/CT scans) should at least be done at the end of every 2 cycles (Day 28 -3days).Imaging can be done more frequently than after every 2 cycles to closely follow up on changes of unknown significance seen on a prior brain MRI or PET/CT scan.
- g. End of treatment assessments to be performed within 7 days after last study agent administration or within 7 days after decision to end treatment. Assessments may continue for ongoing reportable adverse events or events resulting in a dose modification.
- h. A contact/visit for review of adverse events, KPS, concomitant medication review, and vital status is to be performed at 30 days +/- 2 days after the last study agent is given. This may be performed via documented phone conversation with a study nurse or clinician. All participants will be followed until resolution or stabilization of any serious or reportable adverse events occurring during treatment or starting within 30 days of last study agent.
- i. Long-term follow-up to occur until death for updated medical history, RCR testing, and tissue at autopsy. Required elements occur at 3 months (+/-14 days), 6 months (+/-14 days) and annually from start of study treatment, and upon patient death. See footnotes z, rr, and ss for details.
- j. Performed by MD attending only. Informed consent process to be fully documented.
- k. Background/medical history – to include review of treatment history for glioma, any ongoing medical conditions and medical history pertaining to eligibility on study and involvement during study.

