- hh. Imaging to be performed if the prior assessments occurred > 21 days before decision to end treatment, if patient is agreeable to have this procedure. The absence of this MRI and/or PET/CT scan with corresponding response assessment will not be considered a protocol deviation.
- ii. Response assessment using RANO criteria, at time of imaging and as indicated clinically. Dexamethasone dose to be integrated into response determination. See Section 13 for RANO criteria.
- jj. Neurosurgery will include real-time pathology review and may include Rickham Catheter and/or Microdialysis Catheter placement and/or NSC administration. See section 8.2 for details.
- kk. For participants undergoing microdialysis (procedures A, C, E, G, I, K) only, microdialysis catheter is to be removed following completion of microdialysis by the neurosurgical team. See section 8.3.6 for all relevant information.
- ll. On day of surgery, NSC administration will occur either fully during surgical procedure (craniotomy procedure A-J, biopsy procedure A-F), or will occur both during the surgical procedure **and** following the surgical procedure via the Rickham (biopsy procedures G-J only). Half of the participants in the expansion cohort will not receive Day 1 NSCs (procedure K).
- mm. Dose level 2, 3, 4 (procedures E-J) participants only. Via Rickham catheter. See Section 8.5 for procedure.
- nn. For participants undergoing Microdialysis only (procedures A, C, E, G, I, K). Post surgical non-contrast CT used to confirm appropriate placement of catheter. See section 8.3.1 for details.
- oo. For participants undergoing Microdialysis only (procedures A, C, E, G, I, K). Sampling of blood and dialysate to begin prior Day 3 irinotecan administration and up to 48 hours after irinotecan administration. For the blood pKs, a venous catheter is required. See Section 8.3.2 to 8.3.5 for details.
- pp. Irinotecan administration is detailed in Section 8.4, including required prophylaxis, observation periods and documentation for required elements
- qq. (This has been deleted)
- rr. In order to receive Day 3 irinotecan, participant must have recovered well, per the neurosurgeon (documented in clinical record), from any immediate post-operative effects, and the patient must require  $\leq$  16mg/day of dexamethasone. Otherwise the participant will be removed from all study treatments.

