#### 15.1.3 Secondary Objectives

---

- To describe the relationship between hCE1m6-NSC dose and SN-38 concentrations in brain interstitium.
- To characterize the relationship between intracerebral and systemic concentrations of irinotecan and SN-38.
- To investigate the biologic activity of hCE1m6 NSCs by comparing SN-38 concentrations in the brain after treatment with hCE1m6-NSCs and irinotecan versus irinotecan alone.
- To assess for possible development of adenovirally transduced NSC immunogenicity after first exposure and with repeat doses of NSCs.

- To describe the clinical benefit (defined as stable disease, partial response, or complete response) in patients who receive treatment with repeat cycles of NSCs and irinotecan.
- To determine, at time of autopsy, the fate of the NSCs.

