#### 15.1.6 Analysis Plan:

---

Tables will be created to summarize all toxicities and side effects by dose, course, organ severity (by NCI CTCAE version 4.0), and attribution. Rates and associated 95% Clopper Pearson confidence limits will be estimated for DLTs and clinical benefit at the RP2D. Descriptive statistics will be provided for study patient demographics.

Pharmacokinetic data from patients who undergo intracerebral microdialysis will be summarized using descriptive statistics and graphical methods. The biologic activity of the hCE1m6-NSCs, based on comparison of microdialysis SN38 PK data from patients receiving NSCs + irinotecan vs patients receiving irinotecan alone, will be assessed using a one-sided two-sample t test. Regression analysis will be used to assess the relationship between hCE1m6-NSC dose and SN-38 concentrations in brain interstitium using microdialysis data from the patients treated with the initial NSC dose (n=6) and from the patients in the expansion cohort treated with the highest NSC dose (n=4). Other secondary objectives include assessing for possible development of NSC immunogenicity after first and repeat exposures, and—when feasible—evaluating the fate of the NSCs at autopsy. These results will be summarized using descriptive statistics and graphical methods.

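### Stable disease counts as clinical benefit with no minimum duration or earliest scan, so a stable patient who leaves before the first scheduled response scan can be scored as benefit

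*Combined protocol and SAP*

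**What the plan says.** The secondary objective, repeated in Section 15, is to describe "clinical benefit (defined as stable disease, partial response, or complete response) in patients who receive treatment with repeat cycles" of the combination. The Analysis Plan turns this into an estimate: "Rates and associated 95% Clopper Pearson confidence limits will be estimated for DLTs and clinical benefit at the RP2D". It names no minimum exposure and does not carry over the restriction to repeat cycles.

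Section 13, Response Criteria, defines SD as: "Does not qualify for CR, PR, or PD, stable non-enhancing FLAIR/T2 lesions", with the further conditions that the steroid dose is no higher than at baseline and that the patient is clinically stable. The partial response entry there includes "sustained for at least 4 weeks, no progression of non-measurable disease", and complete response carries the same 4-week requirement. SD has no corresponding time element, and I found none elsewhere in the document.

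On timing, Table 10 footnote f says imaging "should at least be done at the end of every 2 cycles". Footnote dd makes the Day 2 MRI the baseline. Footnote hh adds a scan at the end of treatment: "Imaging to be performed if the prior assessments occurred > 21 days before decision to end treatment", provided the patient agrees. Footnote ii attaches a RANO response assessment to imaging.

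**The concern.** SD is the least demanding of the three categories that make up clinical benefit, and the only one with no time requirement. A state definition is harmless if every patient is first assessed at the same planned time. Here the calendar also produces response assessments at the time a patient stops, and these can fall weeks before the first planned one.

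The reported rate could therefore combine patients who stayed stable through two cycles with patients who left sooner and had simply not progressed yet. The second group grows when more patients stop early for toxicity, so poorer tolerability could raise the apparent benefit rate. What is at stake is the meaning of a rate that will be reported with a confidence interval at the RP2D. The dose-finding result is not at stake.

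**Working it through.** **1. Is there a figure to reproduce?** The plan gives no target, assumed rate or power for clinical benefit. The only check available is on the interval method. Section 15, Sample Size, states maximum 95% margins for the DLT rate of 0.38 (n = 6) and 0.27 (n = 14). Clopper-Pearson intervals are widest at x = n/2:

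- 3/6: 0.118 to 0.882, half-width 0.382.
- 7/14: 0.230 to 0.770, half-width 0.270.

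Both stated figures reproduce, so the same method is used below.

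**2. When can SD be scored?**

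- First scheduled response scan: end of cycle 2, 28 + 28 = day 56 (footnote f allows 3 days earlier, so day 53).
- End-of-treatment scan: more than 21 days after the Day 2 baseline MRI, so from 2 + 22 = day 24.
- If the baseline PET/CT (up to 7 days after surgery, so up to day 8) also counts as a prior assessment, the trigger moves to at most 8 + 22 = day 30.
- Start of a second cycle: day 29, or day 31 at dose levels 1 and -1, where cycle 1 lasts 30 days.

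If the objective's restriction means having started cycle 2, the exposed window runs from about day 29 to just before day 56. If the restriction is not applied, as the Analysis Plan's wording permits, the window opens at about day 24.

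**3. Who is scored as benefit in that window?** A patient must satisfy all of the following:

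- stops for a reason other than deterioration (for example systemic toxicity, catheter problems or withdrawal);
- agrees to the end-of-treatment scan;
- does not meet progression;
- is clinically stable, with a steroid dose no higher than at baseline.

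Under footnotes hh and ii and Section 13, that patient is SD and so counts as benefit.

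**4. Size per patient.** The step is 1/n. Two denominators can be read from the document: 14 (Section 15, Sample Size: 6 plus 8), or 8 if the six dose level 4 patients are counted inside the expansion cohort (Section 5, Expansion Cohort).

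- n = 14: 1/14 = 7.1 points.
- n = 8: 1/8 = 12.5 points.

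Limiting the denominator to patients who start a second cycle can only make n smaller and the step larger.

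**5. Illustration.** The counts here are assumptions; the documents give none.

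| Denominator | As written | One early SD not counted | Two not counted |
|---|---|---|---|
| 14 | 4/14 = 28.6% (8.4 to 58.1) | 3/14 = 21.4% (4.7 to 50.8) | 2/14 = 14.3% (1.8 to 42.8) |
| 8 | 3/8 = 37.5% (8.5 to 75.5) | 2/8 = 25.0% (3.2 to 65.1) | not shown |

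**The case against.** The strongest reply is that the exposed group is narrow, and much of that is right.

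- **Population.** The objective concerns patients who receive repeat cycles, which on a plain reading leaves out anyone who stops in cycle 1. This stands, and it is why the main case is a patient who has started cycle 2. But the phrase is not defined or carried into the Analysis Plan, and a gap of up to four weeks before day 56 remains.
- **SD conditions.** SD also needs clinical stability and no steroid increase. Patients who deteriorate do not qualify, and some who stop after a reaction to the cells will have had dexamethasone started or raised. Most toxicities in Table 7.2.4 lead to a hold or reduction, not to stopping. All of this lowers the number affected without making it zero.
- **Scan uptake.** The patient may decline the end-of-treatment scan, and footnote f offers extra scans to follow up uncertain findings, not as a general licence. True, but whether an early leaver is classified then depends on accepting a scan, and the plan does not say how unscanned patients count.
- **Cited criteria.** Section 13 rests on a published response standard that may address SD timing. That cannot be checked here. The protocol's own summary states the time requirement for the two response categories and omits it for SD, so the protocol text supplies no rule.
- **Importance.** The endpoint is descriptive, with no test or decision attached. This stands.

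A reader might also infer that a post-surgical baseline makes SD easy to reach. The documents do not support that. Progression is a rise of at least 25% in enhancing disease or any new lesion, and after debulking a smaller absolute growth reaches 25%; the direction of any effect is not established.

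**Conclusion.** The gap is real and limited. Followed as written, the plan can score as clinical benefit a clinically stable patient who leaves before the first scheduled response scan: from about day 29 if repeat cycles means starting cycle 2, and from about day 24 if that restriction is not applied. Relative to a rule with an earliest qualifying scan, the omission can only add to the numerator, so any bias is upward. Each such patient is worth 7.1 points at n = 14 or 12.5 points at n = 8.

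A reader might infer that every patient who stops in the first weeks will be counted as benefit, or that the rate will be badly inflated. Neither follows. No end-of-treatment scan is triggered before about day 24, the SD conditions exclude patients who deteriorate, and the number of early stable leavers is unknown. Nor does the point touch the RP2D, which rests on dose-limiting toxicity and the toxicity profile.

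This assumes 28-day cycles without delay and a Day 2 baseline MRI.

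**What to change.** In Section 13 (Response Criteria) and Section 15 (Analysis Plan):

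1. Count SD as clinical benefit only when it is documented at or after the scheduled end-of-cycle-2 assessment, including its permitted early window.
2. State the denominator to match the objective: patients at the RP2D who start a second cycle. Those who stop before the end-of-cycle-2 assessment without complete or partial response stay in it as no benefit, whether or not they had an end-of-treatment scan.
3. Show the rate for all patients treated at the RP2D alongside it, and say whether that number is 14 or 8.

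The cost is a few lines of wording; no scan, visit or patient is added. The downside is a somewhat lower reported rate, because a patient who was stable when leaving early no longer counts.

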## 14 DATA REPORTING/PROTOCOL DEVIATIONS

### Data Reporting

#### 14.1.1 Confidentiality and Storage of Records

Electronic Data Collection will be used for this protocol. The data will be stored in encrypted, password protected, secure computers that meet all HIPAA requirements. When results of this study are reported in medical journals or at meetings, identification of those taking part will not be disclosed. Medical records of subjects will be securely maintained in the strictest confidence, according to current legal requirements. They will be made available for review, as required by the FDA, HHS, or other authorized users such as the NCI, under the guidelines established by the Federal Privacy Act and rules for the protection of human subjects.

#### 14.1.2 Subject Consent Form

At the time of registration, the original signed and dated Informed Consent form, HIPAA research authorization form, and the California Experimental Subject's Bill of Rights (for the medical record) and three copies (for the subject, the research record, and the Coordinating Center) must be available. All Institutional, NCI, Federal, and State of California requirements will be fulfilled.

#### 14.1.3 Data Collection Forms and Submission Schedule

All data will be collected using electronic data collection, stored as indicated in Section 14.1.1, and will be submitted according to the timelines indicated in Table 14.1.3.

**Table 14.1.3 Data Submission Schedule**

Form	Submission Timeline
Eligibility Checklist	Complete prior to registration
On Study Forms	Within 14 calendar days of registration
Baseline Assessment Forms	Within 14 calendar days of registration
Treatment Forms	Within 10 calendar days of treatment administration
Adverse Event Report Forms	For cycle 1 only, within 7 calendar days of AE assessment/notification; for all other cycles, within 10 calendar days of AE assessment/notification
Response Assessment Forms	Within 10 calendar days of the response assessment
Other Assessment Forms (concomitant medications, chemistry, hematology, neuro exam, physical exam etc.)	Within 10 calendar days of the assessment
Off Treatment/Off Study Forms	Within 10 calendar days of completing treatment or being taken off study for any reason
Follow up/Survival Forms	Within 14 calendar days of the protocol defined follow up visit date or call

